2.2.5 Clinical Experience

As of October 2009, 10186 subjects had received at least one dose of sunitinib in 84 completed or ongoing clinical studies, (Investigator's Brochure, 2011). In phase 1 studies, sunitinib demonstrated single-agent activity in patients with RCC, GIST, non-GIST sarcomas, non-small cell lung cancer (NSCLC), colorectal cancer, neuroendocrine tumors (NET), melanoma, prostate cancer, and thyroid cancer. Sunitinib has also been studied in the phase 1 setting in patients with acute myeloid leukemia (AML). Sunitinib is approved for use in previously untreated patients with advanced RCC, imatinib-refractory gastrointestinal stromal tumors GIST and unresectable, locally advanced, or metastatic progressive well-differentiated pancreatic neuroendocrine tumors (pNET).

2.2.5.1 Phase 1 Experience

In an early phase 1 study designed to investigate dosing regimen and scheduling (in human

subjects, the results of clinical pharmacology studies demonstrate that C_{max} and area under the concentration-time curve (AUC) increased in a proportional manner after single doses of 50 to 350 mg as well as after multiple doses of 25-100 mg), 41 patients with a variety of advanced solid tumors received sunitinib administered on a schedule of 2 weeks of treatment followed by 2 weeks off (2/2 schedule) or 4 weeks on with 2 weeks off (4/2 schedule).⁴¹ Doses evaluated on the 2/2 schedule (n=23) included 50 mg every other day (n=3), 50 mg daily (n=15), or 75 mg daily (n=5); the 18 patients enrolled in the 4/2 schedule received 25 mg daily (n=3) or 50 mg daily (n=15). The most frequent adverse events (AEs) were constitutional (fatigue/asthenia), gastrointestinal (nausea, vomiting, diarrhea) and hematologic (neutropenia, thrombocytopenia). Most of the AEs were grade 1 or 2, although at 75 mg daily, grade 3 and 4 fatigue/asthenia were dose limiting but readily reversible on discontinuation of treatment. There were 4 partial responses (PRs) assessed by RECIST and 22 patients with stable disease (SD) among the 41 patients.

A phase 1 dose-escalation study in 28 patients with advanced tumors evaluated sunitinib doses of 30 mg/m² every other day, and doses of 30, 42, or 59 mg/m² daily on the 4/2 schedule.⁴² Grade 3 fatigue and hypertension were dose limiting at 59 mg/m² as well as grade 2 bullous skin toxicity, and the MTD was defined as 42 mg/m² daily. Based on these and other reversible AEs in the 12 patients treated at the MTD, the recommended phase 2 dose on the 4/2 schedule was determined to be 50 mg/day. Responses determined by RECIST were seen in 6 of 23 evaluable patients: 3 in RCC, 1 in NET, 1 in GIST, and 1 in adenocarcinoma of unknown primary. Tumor responses in patients treated at higher doses were often associated with reduced intratumoral vascularization and central tumor necrosis, leading to organ perforation in one patient and fistula in another. These observations suggest the possible necessity for careful tumor density monitoring to detect early evidence of necrosis.

Two phase 1 studies have been conducted in AML, the first with the primary endpoint of evaluation of the inhibition of FLT3 phosphorylation and the second designed as a conventional dose-escalation study.^{43,44} O'Farrell and colleagues studied FLT3 phosphorylation in 29 AML patients who received a single dose of sunitinib at doses ranging from 50-350 mg. Over 50% of patients showed strong inhibition of Flt3 phosphorylation at doses of 200 mg and higher. As anticipated from nonclinical data, patients with FLT3 internal tandem duplication (ITD) mutations were more sensitive than those with wild-type Flt3 (FLT3-WT) as shown by 100% inhibition in FLT3-ITD compared to 50% in FLT3-WT. This study also gave evidence of downstream signal inhibition (STAT5 and ERK pathways), with STAT5 levels reduced primarily in FLT3-ITD patients while ERK inhibition occurred in the majority of patients independently of FLT3 inhibition. The dose-escalation study enrolled 15 patients with refractory or resistant AML who were treated with sunitinib on either the 4/2 or 4/1 schedule at a starting dose of 50 mg/day. Dose-limiting AEs (grade 4 fatigue and hypertension) occurred in both patients treated at 75 mg/day, and one of these patients (who had received prior mitoxantrone) developed cardiac failure. The 75 mg dose level was therefore terminated and 50 mg/day was considered to be the MTD. All four patients with FLT3 mutations had morphologic or partial responses compared to 2 of 10 evaluable patients with wild-type FLT3. Responses, although longer in patients with mutated FLT3, were of short duration.

Preliminary results from phase 1 studies exploring the combination of sunitinib with chemotherapeutic agents like capecitabine,⁴⁵ pemetrexed,⁴⁶ docetaxel,⁴⁷ gemcitabine,⁴⁸ carboplatin/paclitaxel,⁴⁹ and metronomic cyclophosphamide/ methotrexate⁵⁰ in patients with various solid tumors have been presented. The MTD of sunitinib on the 4/2 schedule with docetaxel (60 mg/m²) was 25 mg daily; with capecitabine (1000 mg/m²), it was 37.5 mg daily. The MTD of sunitinib on the 2/1 schedule with docetaxel (75 mg/m²) was 37.5 mg daily and with capecitabine (1000 mg/m²) was 50 mg daily. The MTD for sunitinib as continuous daily dosing (CDD) with capecitabine (1000 mg/m²) was 37.5 mg daily and for pemetrexed (500 mg/m²) was 37.5 mg daily. Reported DLTs included febrile neutropenia, fatigue, hand-foot syndrome, gastrointestinal hemorrhage, cerebral hemorrhage, and ischemic optic neuropathy. Phase 1 trials evaluating the combination of sunitinib with other targeted agents like temsirolimus,⁵¹ bevacizumab⁵² and IFN- α ⁵³ have shown problems with increased toxicity in patients with RCC.⁵⁴

2.2.5.2 Phase 2 and 3 Experience

Updated results have recently been published on 750 patients with MRCC treated on a phase 3 study of sunitinib at a daily dose of 50 mg on the 4/2 schedule compared to interferon (IFN)- α 9 MU subcutaneously thrice weekly.⁵⁵ Median overall survival (OS) was greater in the sunitinib group than in the IFN- α group (26.4 vs. 21.8 months, respectively). Sunitinib treatment was associated with a higher objective response rate (RR) than IFN- α (47% vs. 12%, respectively). Eleven patients in the sunitinib group and four patients in the IFN- α group achieved a complete response per investigator assessment. Median progression-free survival (PFS) was 11 months for sunitinib compared with 5 months for IFN- α . The most commonly reported sunitinib-related grade 3 adverse events included hypertension (12%), fatigue (11%), diarrhea (9%), and hand-foot syndrome (9%). An exploratory analysis, which censored 25 patients from the IFN- α group who had crossed over to receive sunitinib on study, showed a median OS time of 26.4 months for sunitinib compared with 20 months for the IFN- α group. Results from a phase 1/2 dose-finding trial of sunitinib plus gefitinib, enrolling 42 patients, have been published.⁵⁶ In phase 1, patients received sunitinib 37.5 or 50 mg on the 4/2 schedule plus gefitinib 250 mg, both once daily. The MTD was determined to be 37.5 mg. Two DLTs were observed with the 50 mg dose: grade 2 left ventricular ejection fraction decline and grade 3 fatigue. In phase 2, patients received sunitinib at the MTD plus gefitinib. Thirteen patients treated at the MTD achieved a partial response and 12 had stable disease. Median PFS was 11 months. The most commonly reported grade 3/4 adverse event was diarrhea.

The promising results in phase 1 trials and the involvement of KIT and PDGFR- α , two of the sunitinib target RTKs in GIST led investigators to undertake a phase 1/2 trial in patients with GIST refractory or intolerant to imatinib to determine an appropriate dose and regimen for phase 2 development of sunitinib in this disease. Patients received up to 75 mg sunitinib daily on the 2/2, 4/2, or 2/1 schedule, with 50 mg daily on the 4/2 schedule being selected for continued study. In all, 75 patients were treated on the trial. Among 41 patients treated for at least 6 months, 6 had an objective response (OR; RECIST criteria) and an additional 16 had cessation of disease progression and minor responses for >6 months. Overall, 54% of the 41 patients had evidence of clinical benefit (OR or PFS). Determination of the GIST genotype in these 41 patients showed that clinical benefit had been achieved in several secondary mutational variants

that conferred imatinib resistance.⁵⁷ Fifty-three of the GIST patients treated on this trial subsequently underwent serial ¹⁸FDG-PET imaging where qualitative responses were graded as good in 33/53 patients, mixed in 15/53, and poor in 5/53.⁵⁸ Correlation with clinical response (Fisher's exact p=0.03) showed that 22 of 33 patients graded as good by ¹⁸FDG-PET imaging had clinical benefit (OR or SD \geq 6 months) after 6 months of therapy while 4 of 15 patients graded as mixed had benefit as did 2 of 5 patients graded as poor.

Data from a pivotal multinational, randomized (2:1), double-blind, placebo-controlled phase 3 trial in over 300 patients with imatinib-resistant GIST has shown significant clinical effect with sunitinib compared with placebo.⁵⁹ Patients on the active treatment arm received sunitinib at a dose of 50 mg daily on the 4/2 schedule. The median TTP for the treatment arm (n=207) was 27.3 weeks compared to a median of 6.4 weeks for placebo (n=105) (p<0.0001). Therapy was reasonably well tolerated; the most common adverse events were fatigue, diarrhea, skin discoloration and nausea.

In addition to patients with RCC and GIST, sunitinib has been evaluated in breast cancer,⁶⁰ NSCLC,⁶¹ transitional cell carcinoma (TCC),⁶² NET⁶³, thyroid carcinoma,⁶⁴ certain subtypes of sarcoma,⁶⁵ gastro-esophageal cancer,⁶⁶ high-grade glioma,⁶⁷ squamous cell carcinoma of the head and neck (SCCHN),⁶⁸ hepatocellular carcinoma (HCC) (Zhu *et al.*, 2008),⁶⁹ colorectal carcinoma (CRC)⁷⁰ and uveal melanoma.⁷¹

2.2.5.3 Safety Profile

Sunitinib is reasonably well tolerated, with asthenia, hypertension, dermatitis, and mild myelosuppression as the most common AEs.⁷² Additionally, the inhibition of TK receptors by agents such as sunitinib can result in cutaneous AEs such as acral erythema, subungual splinter hemorrhages, modification of hair and skin pigmentation, mucositis, and (occasionally) periocular edema.^{73,74} Hand-foot skin reaction, a group of signs and symptoms that can affect, usually bilaterally, the hands and/or feet of patients, has occurred in patients receiving sunitinib. A recent analysis of dermatological AEs in patients receiving sunitinib therapy has reported that all-grade hand-foot skin reactions occurred in 19% of patients (5% grades 3-4), skin discoloration in 28% (no grades 3-4), dry skin in 16% (1% grades 3-4), skin rash in 13% (1% grades 3-4), dermatitis in 8% (2% grades 3-4), hair color changes in 10% (no grades 3-4), alopecia in 6% (no grades 3-4), and phototoxicity in <0.1% (no grades 3-4) (Rosenbaum *et al.*, 2008).

Cardiotoxicity, including congestive heart failure (3%-8%) and left ventricular dysfunction (12%-14%), has been reported in patients undergoing treatment with sunitinib.⁷⁵⁻⁷⁸ More subjects treated with sunitinib experienced decline in left ventricular ejection fraction (LVEF) than subjects receiving either placebo or IFN- α (Investigator's Brochure, 2011). In a phase 3 GIST study in subjects with imatinib-resistant or -intolerant GIST, 22 of 209 (11%) subjects on sunitinib and 3 of 102 (3%) subjects on placebo had treatment-emergent LVEF values below the lower limit of normal (LLN). In a phase 3 study treatment-naive RCC patients, 27% and 15% of subjects on sunitinib and IFN- α , respectively, had an LVEF value below the LLN. Among 461 patients enrolled in CDUS-monitored trials with sunitinib alone, 2% of patients experienced left ventricular systolic dysfunction (CDUS data). It is unknown whether patients with concurrent

cardiac conditions may be at a higher risk for developing drug-related LVEF. Baseline and periodic evaluations of LVEF should be considered while these patients are on sunitinib treatment. In patients without cardiac risk factors, a baseline evaluation of LVEF should be considered.

Sunitinib has been shown to prolong the QT interval in a dose-dependent manner, which may lead to an increased risk for **ventricular arrhythmias**, including Torsade de Pointes. This condition has been reported in <0.1% of sunitinib-exposed patients. The DCTD, NCI, issued an IND AE Action Letter to all investigators using sunitinib describing the occurrence of QTc prolongation and Torsade de pointes (ventricular tachycardia) in patients on clinical trials utilizing sunitinib. As a result of this Action Letter, DCTD, NCI-sponsored sunitinib protocols were amended to include the requirement for a baseline EKG prior to study treatment, exclude patients with histories of serious ventricular arrhythmias or prolonged QTc, and exclude patients with certain cardiac conditions.

Among 8832 solid tumor subjects treated with single-agent sunitinib, Grade 3 **hypertension** was reported in 6.8% of patients and was one of the most commonly reported Grade 3 AEs. Of subjects receiving sunitinib for treatment-naïve MRCC, 34% receiving sunitinib experienced hypertension, compared with 4% on IFN- α . Grade 3 hypertension was reported in 13% of treatment-naïve metastatic RCC subjects on sunitinib compared to <1% on IFN- α . Severe hypertension occurred in 4% GIST subjects on sunitinib, 1% GIST subjects on placebo, 9% RCC subjects on sunitinib and 1% RCC subjects on IFN- α (Investigator's Brochure, 2011). Among 516 patients enrolled in CDUS-monitored trials with sunitinib alone, 33.9% experienced hypertension (CDUS data).

In subjects receiving sunitinib for treatment-naïve MRCC, 37% had **bleeding events** compared with 8% receiving IFN- α (Investigator's Brochure, 2011). Bleeding events occurred in 18% of patients receiving sunitinib in the double-blind treatment phase of the GIST phase 3 study, compared with 17% receiving placebo. Among 516 patients enrolled in CDUS-monitored trials with sunitinib alone or in combination with other agents, there were 123 reported bleeding events (CDUS data). Epistaxis was the most common hemorrhagic AE reported. Tumor-related hemorrhage can occur with sunitinib and in the case of pulmonary tumors, may present as severe and life-threatening hemoptysis or pulmonary hemorrhage.

Hypothyroidism has been reported in 71% patients with RCC and in 36% of those with GIST treated with sunitinib.⁷⁹ Among 8832 subjects with solid tumors treated with single-agent sunitinib as of October 2009, 978 (11.1%) experienced treatment-emergent hypothyroidism. Among subjects treated with single-agent sunitinib, hyperthyroidism was reported in 0.7% and thyroiditis in 0.1% (Investigator's Brochure, 2011). Baseline measurement of thyroid function is recommended, and patients with thyroid dysfunction should be treated appropriately prior to starting sunitinib therapy.

Nonclinical evidence of **adrenal toxicity** following sunitinib exposure led the company to perform specialized safety assessments in clinical studies, including computed tomography or MRI in 336 subjects to specifically identify any change in adrenal gland structure or the presence

of adrenal gland hemorrhage (Investigator's Brochure, 2011). Neither event was observed. Adrenocorticotrophic hormone (ACTH) stimulation testing was done in 400 patients across multiple sunitinib trials. One subject developed consistently abnormal test results during treatment that were unexplained and may be related to sunitinib treatment. Eleven additional subjects had abnormalities in the final test, with low peak cortisol levels. None of these patients had clinical evidence of adrenal insufficiency. However, based on the nonclinical findings, patients receiving sunitinib should be clinically followed for signs and symptoms of adrenal insufficiency, especially in (1) patients with comorbidities associated with adrenal dysfunction, (2) patients with preexisting adrenal insufficiency (primary or secondary), and (3) patients with concomitant stress (e.g., fever, infection, bleeding, serious accident, surgery) that may precipitate overt adrenal insufficiency in the presence of subclinical sunitinib-induced adrenal toxicity.

Diarrhea, nausea, abdominal pain, vomiting, constipation and dyspepsia are some of the most frequent AEs reported with sunitinib (Investigator's Brochure, 2011). Serum chemistries including phosphate should be performed at the beginning of each treatment cycle. Supportive care may include anti-emetic premedication, supportive oral care products, and analgesics. Serious complications due to degeneration or shrinkage of tumors, including gastrointestinal perforation and tracheoesophageal fistula, have occurred rarely in patients with abdominal, head and neck, thyroid, and other malignancies treated with sunitinib, believed to be the result of the antitumor effect of sunitinib. Other serious effects include thromboembolic events, rare reversible posterior leukoencephalopathy syndrome (RPLS), proteinuria with rare nephrotic syndrome, and rare microangiopathic hemolytic anemia.

Alternative dosing schedules

Due to the toxicity associated with the standard dosing (50 mg per day for 4 weeks followed by a 2-week break) alternative dosing schedules have been explored. Superior tolerability has been demonstrated with a 2-weeks on and 1-week off schedule in patients with metastatic renal carcinoma.^{80,81}

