3 PATIENT SELECTION

3.1 ELIGIBILITY CRITERIA

- 3.1.1 Histological confirmation of thymoma (Group 1 only) or thymic carcinoma by the pathology department/CCR/NCI or the pathology department of participating institutions.
- 3.1.2 At least one prior line of platinum-based chemotherapy or patient must have refused

cytotoxic chemotherapy. Progressive disease must be documented prior to study entry.

- 3.1.3 Patients must not have received chemotherapy, radiation therapy, or undergone major surgery within 4 weeks prior to enrollment.
- 3.1.4 Patients must have measurable disease, per RECIST 1.1. See Section 12 for the evaluation of measurable disease.
- 3.1.5 Age ≥ 18 years
- 3.1.6 ECOG performance status ≤ 2 (Karnofsky $>50\%$, see Appendix A).
- 3.1.7 Life expectancy of greater than 3 months
- 3.1.8 Patients must have normal organ and marrow function as defined below:
- | | |
|-----------------------------|--|
| - hemoglobin | ≥ 9 g/dL |
| - leukocytes | $\geq 3,000$ /mcL |
| - absolute neutrophil count | $\geq 1,200$ /mcL |
| - platelets | $\geq 100,000$ /mcL |
| - total bilirubin | within normal institutional limits |
| - serum calcium | ≤ 12.0 mg/dL |
| - AST(SGOT)/ALT(SGPT) | $\leq 2.5 \times$ institutional upper limit of normal* |
| - creatinine | within normal institutional limits |
- OR
- | | |
|--|--|
| - creatinine clearance | ≥ 60 mL/min/1.73 m ² for patients with creatinine levels above institutional normal. |
| - * If subjects have liver metastases, both ALT and AST must be $\leq 5 \times$ ULN. | |
| - Patients must have QTc < 500 msec | |
- 3.1.9 PT or INR, and APTT $\leq 1.5 \times$ upper limit of normal (ULN), unless the abnormality can be explained by the presence of lupus anticoagulant or if these values are in the therapeutic range for a patient on low molecular weight heparin.
- 3.1.10 The following groups of patients are eligible provided they have New York Heart Association Class II (NYHA; see Appendix B) cardiac function on baseline ECHO/MUGA:
- those with a history of Class II heart failure who are asymptomatic on treatment
 - those with prior anthracycline exposure
- those who have received central thoracic radiation that included the heart in the radiotherapy port.
- 3.1.11 Patients must have blood pressure (BP) no greater than 140 mmHg (systolic) and 90

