3.2 EXCLUSION CRITERIA

- 3.2.1 Patients with tumor amenable to potentially curative therapy.
- 3.2.2 Prior treatment within the past 6 months with sunitinib, sorafenib, bevacizumab or other multikinase inhibitors targeting any of the following: vascular endothelial growth factors 1–3 (VEGF1–3), FMS-like tyrosine kinase 3 (FLT3), stem cell growth factor (c-KIT), platelet-derived growth factors- α and - β (PDGF- α , - β), colony-stimulating factor 1 (CSF1), and the ‘RET’ receptor for glial-derived neurotrophic factors.
- 3.2.3 Patients with symptomatic brain metastases will be excluded from trial secondary to poor prognosis. However, patients who have had treatment for their brain metastasis and whose brain disease has remained stable for 3 months without steroid therapy may be enrolled.
- 3.2.4 Patients with evidence of severe or uncontrolled systemic disease, or any concurrent condition, which could compromise participation in the study, including, but not limited to, active or uncontrolled infection, immune deficiencies, uncontrolled HBV and/or HCV infection unless sustained virologic response to HCV therapy, uncontrolled diabetes, serious non-healing ulcer, wound or bone fracture, history of intra-abdominal abscess, abdominal fistula or gastrointestinal perforation within 28 days of treatment, history of pulmonary embolism in the past 12 months, uncontrolled hypertension, myocardial infarction, cardiac arrhythmia, stable/unstable angina, symptomatic congestive heart failure, or coronary/peripheral artery bypass graft or stenting within 12 months prior to

study entry, Class III or IV heart failure as defined by the NYHA functional classification system (see [Appendix B](#)), stroke/cerebrovascular accident or transient ischemic attack within the past 12 months or psychiatric illness/social situations which would jeopardize compliance with the protocol.

- 3.2.5 History of a previous invasive malignancy within the last 5 years, except adequately treated non-melanoma skin cancer, papillary carcinoma of the thyroid or carcinoma in situ of the uterine cervix.
- 3.2.6 Patients who have had chemotherapy or radiotherapy within 4 weeks (6 weeks for nitrosoureas or mitomycin C) prior to entering the study or those who have not recovered from adverse events due to agents administered more than 4 weeks earlier.
- 3.2.7 Patients who are receiving any other investigational agents.

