- 3.2.8 History of allergic reactions attributed to compounds of similar chemical or biologic composition to sunitinib.

Patients receiving any medications or substances that are strong inhibitors or inducers of CYP3A4 are ineligible. (A list of potent CYP3A4 inducers or inhibitors can be found in Section 5.2) An exception will be made for patients who are on ritonavir-based highly active antiretroviral therapy, in which case the starting dose of sunitinib will be modified as indicated in Sections 5.2.11. Every effort should be made to switch patients taking such agents or substances to other medications. A comprehensive list of medications and substances known or with the potential to alter the pharmacokinetics of sunitinib through CYP3A4 is provided in [Appendix C](#).

- 3.2.9 Pregnant women are excluded from this study because sunitinib angiogenesis inhibitor with the potential for teratogenic or abortifacient effects. Because there is an unknown but potential risk for adverse events in nursing infants secondary to treatment of the mother with sunitinib breastfeeding should be discontinued if the mother is treated with sunitinib.
- 3.2.10 Patients who require therapeutic doses of Coumadin derivative anticoagulants such as warfarin are excluded. Low molecular weight heparin is permitted, provided the patient's PT/INR is ≤ 1.5 . Coumadin doses of up to 2 mg daily are permitted for prophylaxis of thrombosis.
- 3.2.11 Patients with a pre-existing thyroid abnormality who are unable to maintain thyroid function in the normal range with medication are ineligible.
- 3.2.12 Patients with any condition (e.g., gastrointestinal tract disease resulting in an inability to take oral medication or a requirement for IV alimentation, prior surgical procedures affecting absorption, or active peptic ulcer disease) that impairs their ability to swallow

and retain sunitinib tablets are excluded.

3.2.13 Patients with QTc prolongation (defined as a QTc interval equal to or greater than 500 msec) or other significant ECG abnormalities are excluded.

3.2.14 Patients with poorly controlled hypertension (systolic blood pressure of 140 mmHg or higher or diastolic blood pressure of 91 mmHg or higher) are ineligible.

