5.2.10 Use of agents with proarrhythmic potential (terfenadine, quinidine, procainamide, disopyramide, sotalol, probucol, bepridil, haloperidol, risperidone, indapamide, and flecainide) is not permitted during treatment with sunitinib. A comprehensive list of agents with proarrhythmic potential can be found at <http://torsade.org>.

5.2.11 **Cytochrome P450-3A4 (CYP3A4) inhibitors and/or inducers:** Patients must not have received potent inhibitors within 7 days and potent inducers within 12 days prior to drug administration.

Sunitinib is primarily metabolized by liver enzymes, in particular CYP3A4. There was a mean 1.8-fold increase in exposure of SU011248 when co-administered with ketoconazole, a strong inhibitor of CYP3A4 and a mean 4-fold decreased in exposure of SU011248 when co-administered with rifampin, a strong inducer of CYP3A4.

Therefore, co-administration with strong inhibitors (grapefruit/grapefruit juice, ketoconazole, itraconazole, clarithromycin, indinavir, saquinavir, ritonavir, atazanavir, nelfinavir, nefazodone, voriconazole, telithromycin) and strong inducers (dexamethasone, rifampin, rifabutin, rifapentin, carbamazepine, phenobarbital, phenytoin, St. John's wort) of CYP3A4 may result in significant increases/decreases in exposure of SU011248 and may alter the safety/efficacy of the drug. However for patients who are on ritonavir, sunitinib may be administered at a starting dose of 37.5 mg q day.¹⁴²

Strong CYP3A4 inhibitors and inducers are not permitted 7 and 12 days before dosing, respectively. During the study, strong CYP3A4 inhibitors and inducers are not recommended. Alternative therapies should be used when available. If usage of a strong CYP3A4 inhibitor or inducer is necessary, this must be in agreement with the Sponsor. The following drugs should not be used before or during the study:

Inhibitors – prohibited 7 days before dosing and during study.

azole antifungals (ketoconazole, itraconazole)	diltiazem
clarithromycin	verapamil
erythromycin	

Inducers – prohibited 12 days before dosing and during study.

rifampin	phenobarbital
rifabutin	phenytoin
carbamazepine	St. John's wort

Aprepitant, fluconazole and voriconazole are clinically relevant moderate CYP3A4 inhibitors that should be avoided, if possible, or used with great caution.

Additional inducers or inhibitors of CYP3A4 can be found at <http://medicine.iupui.edu/clinpharm/ddis>. Interacting drugs with sunitinib should be avoided or used with great caution.

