6.7 MANAGEMENT OF OTHER CLINICALLY SIGNIFICANT SUNITINIB-RELATED AEs

(not specifically addressed above)

Observation	Action
AE resolves promptly with supportive care	Maintain dose level
1. Grade 3 or higher (non-hematologic or grade 4 (hematologic) AE related to sunitinib and lasting >5 days that does not resolve to grade 2 or below despite maximum supportive care for < 48 hours.	Reduce one dose level
AE does not resolve to grade 2 or below after treating patient at the lowest (i.e., 25* mg or 12.5* daily) reduced dose level.	In general, remove patient from study**
* 25 mg if the patients start dosing at 50 mg on a 4/2 schedule (solid tumors) or 12.5 mg if patients start dosing at 37.5 mg ** After consultation with study sponsor (DCTD, NCI), a dose of 25 mg daily may be considered for patients on study ≥ 3 months who are benefiting from the agent.	

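### Section 3 does not clearly exclude a past serious ventricular arrhythmia, although the protocol says sunitinib trials of this sponsor were amended to do so

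*Combined protocol and SAP*

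**What the plan says.** Section 2.2.5.3 (Safety Profile) describes dose-dependent QT prolongation with sunitinib and the resulting risk of ventricular arrhythmia. It then reports an Action Letter to investigators, after which DCTD, NCI-sponsored sunitinib protocols were amended in three ways: to require a baseline EKG, to "exclude patients with histories of serious ventricular arrhythmias or prolonged QTc", and to exclude certain cardiac conditions. No time limit is given for the arrhythmia history. A footnote in Section 6.7 shows that this trial falls in that family of protocols: "After consultation with study sponsor (DCTD, NCI".

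The criteria in Section 3 that bear on the point are these:

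- 3.2.4 excludes severe or uncontrolled systemic disease, or "any concurrent condition, which could compromise participation in the study, including, but not limited to" a long list. Part of that list reads "cardiac arrhythmia, stable/unstable angina, symptomatic congestive heart failure, or coronary/peripheral artery bypass graft or stenting within 12 months" before study entry.
- 3.1.8 requires a QTc limit at entry: "Patients must have QTc < 500 msec".
- 3.2.13 excludes a QTc of 500 msec or more; patients with this "or other significant ECG abnormalities are excluded".
- 3.1.10 deals with NYHA class only.

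Section 18.1, which explains the exclusions, restates the arrhythmia item as uncontrolled arrhythmia.

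**The concern.** The background section describes an exclusion based on history. The eligibility section tests the current ECG and lists arrhythmia of unspecified type, apparently with a 12-month limit. Sites enrol from Section 3, so a requirement that appears only in the background has no effect at screening.

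Patient safety is at stake. The EKG is scheduled pre-study only in both study calendars (Section 11). The QTc dose-modification rules in Section 6.6 therefore depend on on-treatment EKGs that the calendars do not plan. That makes entry screening the main planned point at which a susceptible patient would be identified. The statistical design is not involved.

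**Working it through.** **Step 1: does the background requirement apply here?** Section 2.2.5.3 refers to DCTD, NCI-sponsored sunitinib protocols. Section 6.7 names DCTD, NCI as study sponsor. It applies.

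**Step 2: run a test case through Section 3.** Take a candidate with a resolved serious ventricular arrhythmia more than 12 months before entry, a normal baseline EKG and QTc below 500 msec.

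| Criterion | Result for the test case |
|---|---|
| 3.1.8 (QTc) | Met |
| 3.1.10 (NYHA function) | Does not address arrhythmia |
| 3.2.13 (QTc, ECG abnormalities) | Not triggered; it concerns current findings |
| 3.2.4, window covers arrhythmia | Not triggered; the event is too old |
| 3.2.4, window covers only bypass or stenting | Unclear; the lead-in concerns severe, uncontrolled or concurrent conditions, and the event is resolved |

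The first reading of 3.2.4 is the more natural. Myocardial infarction stands immediately before arrhythmia in the same run and has no other window, and Section 18.1 gives infarction a time limit (6 months there). A window that reaches back to infarction also covers arrhythmia. Where a separate limit was wanted, the list states one, as in "history of pulmonary embolism in the past 12 months". Under either reading the test case is not clearly excluded.

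**Step 3: how many patients could this affect?** Section 17.2 says Group 1 accrual is complete. Section 17.1 allows up to 15 patients in Group 2, so n = 15 is an upper limit. The documents give no prevalence, so two inputs are assumed:

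- p, the share of candidates with any serious ventricular arrhythmia history: 0.5% to 2%.
- f, the fraction of those whose event is resolved and more than 12 months old, with a normal EKG and no barred drug: 25% to 75%.

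Then q = p × f, expected number = n × q, and P(at least one) = 1 − (1 − q)^n.

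| Case | q | Expected in 15 | P(at least one) |
|---|---|---|---|
| Low | 0.005 × 0.25 = 0.00125 | 15 × 0.00125 = 0.019 | 1 − 0.99875^15 = 1.9% |
| Middle | 0.01 × 0.50 = 0.005 | 15 × 0.005 = 0.075 | 1 − 0.995^15 = 7.2% |
| High | 0.02 × 0.75 = 0.015 | 15 × 0.015 = 0.225 | 1 − 0.985^15 = 20.3% |

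These are chances of enrolling such a patient. Section 2.2.5.3 puts Torsade de Pointes below 0.1% of exposed patients overall. The risk given a prior ventricular arrhythmia is not stated, so harm cannot be estimated.

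**The case against.** **The benchmark is second-hand.** The Action Letter is not in the documents. Section 2.2.5.3 gives a one-sentence summary, and silence on timing does not prove that there was no time limit. If the letter allowed 12 months, 3.2.4 already complies. This stands as a limit on certainty, and the fix allows for it.

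**Every element of the summary has a counterpart.** A baseline EKG is scheduled, QTc is tested, and 3.2.4 names arrhythmia of any type, which is broader than serious ventricular arrhythmia. This is true for current or recent arrhythmia. It does not reach an older, resolved event.

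**3.2.4 can be read more widely.** The window directly follows bypass and stenting, some listed items are present states that fit a look-back poorly, and the open-ended lead-in lets an investigator exclude by judgement. The wider reading is possible, but Section 18.1's reference to uncontrolled arrhythmia tells against it. Discretion permits exclusion without requiring it.

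**Other safeguards exist.** A pre-study medical history is required (Section 11) and eligibility is confirmed centrally (Section 4). "Use of agents with proarrhythmic potential" is barred in 5.2.10, diltiazem and verapamil are prohibited in 5.2.11, and 5.1.3 requires a baseline ECHO or MUGA for everyone. Section 6.6 sets QTc actions above 450 msec and at 550 msec or more. These reduce the exposure. However, the history and central checks apply the criteria as written, and none of the written criteria asks about past ventricular arrhythmia.

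**Few slots may remain.** Group 2 opened with Amendment E in May 2014, with about one further year of accrual expected (Section 17.2). The reviewed version is dated April 2020. The documents do not say that accrual has closed, but if it has, the effect on enrolment is nil.

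**Conclusion.** The concern holds as a minor patient-safety point. On the natural reading of 3.2.4, a site following Section 3 could enrol a patient whom the protocol's own account of the sponsor's requirement would exclude.

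The likely size is very small: well under one expected patient across the whole assumed range, and possibly none if Group 2 is full. The conclusion about the wording rests on the summary in Section 2.2.5.3 being an accurate account of the letter. The size rests on the assumed prevalences and on 15 as an upper limit.

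The conclusion covers only the ventricular-arrhythmia part of the requirement. The prolonged-QTc part may already be met by 3.1.8 and 3.2.13, if the letter meant QTc at entry.

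**What to change.** Add to 3.2.13, and to the registration eligibility checklist, an exclusion for any history of serious ventricular arrhythmia, defined as ventricular tachycardia, ventricular fibrillation or Torsade de Pointes. Leave the 12-month window in 3.2.4 for the other cardiac items. The sponsor should check the Action Letter: if it set a look-back period, state that period in the new criterion. Add a clause on past QTc prolongation only if the sponsor confirms that the letter meant past values.

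The cost is one eligibility sentence and one checklist line, with the possible loss of a rare candidate in a rare disease.
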